8.2 Secondary Outcomes

8.2.1 Patient reported outcomes

Patient-reported outcomes (PROs), related to pain, fatigue, functional ability, anxiety, depression, global health, family impact, and other medication side effects will be collected and analyzed. PROMIS® measures will be used for each of the outcomes of interest where available. Caregiver/proxy-report will be obtained for participants able to complete the forms in English or in Spanish, and by self-report for children ≥ 8 years of age. The existing iPAD-based, CARRA Registry electronic PRO system will be utilized.

The following PRO instruments will be used.

- PROMIS® pediatric measures selected by the patient/family partners (pain interference, fatigue, functional ability) that have undergone preliminary validation in JIA.^{64,65}
- PROMIS® pediatric measures of anxiety, depression, and global health.
- Side effects of medications, assessed by the yes/no question 11 in the JAMAR.⁶⁶

Table 5: Description of PROs

Outcome	Measure	Timing	Source
Pain	PROMIS® pediatric pain interference	Every study visit	Parent-proxy or child (if \geq 8 years)
Fatigue	PROMIS® pediatric fatigue; short form	Every study visit	Parent-proxy or child (if \geq 8 years)
Functional Ability	PROMIS® upper extremity function and mobility	Every study visit	Parent-proxy or child (if \geq 8 years)
	CHAQ	Baseline, 6M, 12M	Parent-proxy or child (if \geq 8 years)
Anxiety	PROMIS® pediatric emotional distress – anxiety; short form	Baseline, 6M, 12M	Parent-proxy or child (if \geq 8 years)
Depression	PROMIS® pediatric emotional distress – depression; short form	Baseline, 6M, 12M	Parent-proxy or child (if \geq 8 years)
Global Health	PROMIS® pediatric global health measure (PGH-7)	Every study visit	Parent-proxy or child (if \geq 8 years)
Other medication side effects	JAMAR (Juvenile Arthritis Multidimensional Arthritis Report) question #11	Baseline, 3M, 6M	Parent-proxy or child (if \geq 8 years)

8.2.2 Enhanced Study Recruitment (US Based Sites Only)

The outcome for screening efficacy using enhanced study recruitment will be assessed as the marginal difference for successful identification of study participants who meet the limited JIA inclusion criteria. We will compare absolute and relative numbers of eligible participants identified by computable phenotype augmented screening lists vs screening lists generated by current, ad-hoc processes alone. In addition, the efficiency of augmented screening will be assessed as the number of additional records requiring manual screening and chart review in order to identify one additional eligible participant.

8.2.3 Data Completeness

The main outcome for data completeness will be the rate of missing data utilizing same-site comparison. We will assess and compare the relative differences in data completeness by data elements of interest (i.e. hospitalizations, abnormal lab values of interest, occurrence of infections) before and after EHR data linkage at participating sites. Additional outcomes may include metrics of research coordinator time required to achieve various thresholds of data

completeness across sites that utilize data linkage in comparison to sites that do not employ data linkage. For sites not employing data linkage, study data of representative samples of enrolled study participants may be analyzed via chart review of EHR data to estimate the completeness of data.

8.2.4 Other Secondary Outcomes

Other outcomes describing the clinical course of study participants will include

- Proportion of children achieving clinical inactive disease and/or remission
- Number of new joints with arthritis.
- Cumulative number of glucocorticoid joint injections.
- Serious adverse events.
- Juvenile arthritis disease activity (JADAS) scores.
- Elapsed time from enrollment to disease extension, uveitis or systemic medication use.
- Proportion of participants with disease extension (development of polyarthritis or uveitis).

9 STATISTICAL ANALYSIS PLAN AND DETERMINATION OF SAMPLE SIZE

9.1 Statistical Design

The primary objective of LIMIT-JIA is to evaluate the effectiveness of a 24-dose course of abatacept (Orencia) plus usual care (including NSAIDs and/or intra-articular glucocorticoids) versus usual care alone, to prevent development of polyarthritis or uveitis, or initiation of treatment with other systemic medication(s) for JIA (i.e. one or more of the following: systemic glucocorticoids, DMARD or biologic) within 12 months of enrollment in children with recent-onset limited JIA.

Secondary objectives include comparison of participants and caregiver reported outcomes between the different treatment strategies.

The analysis population will include data from two parts of Limit-JIA. In Part I participants were randomly assigned to receive abatacept + usual care or usual care alone. Part II participants will all be assigned to receive abatacept + usual care.

Part I enrolled participants into a randomized open-label multicenter trial with a planned sample size of 306 JIA participants recruited from CARRA Registry sites. Participants were randomly allocated (1:1) to receive 24 weeks of abatacept plus usual care or usual care alone.

Randomization was stratified on uveitis risk (higher and lower) and polyarthritis risk (higher and lower). Upon completion of 24 weeks of randomized treatment, each participant was to receive usual care and undergo follow-up for assessment of outcomes for an additional 12 months.

Planned duration of the study for each participant was 18 months. Due to slow accrual and apparent loss of equipoise, enrollment into Part I has been discontinued 17February2022. As of October 29, 2021, 37 participants have been randomized in Part I. Part I participants will continue follow-up as planned.

Part II is a non-randomized continuation of LIMIT-JIA with planned enrollment of 80 evaluable participants receiving abatacept. Participants will receive 24 doses of abatacept plus usual care. Upon completion of 24 doses, each participant will receive usual care and undergo follow-up for assessment of outcomes for an additional 6 months. Planned duration of the study for each participant is 12 months. Part II will assess the efficacy of abatacept in prevention of disease extension by comparison of outcomes between participants enrolled in the abatacept arm and 428 CARRA Registry patients who would have met major eligibility criteria for LIMIT-JIA.

Statistical analysis of this study is planned upon study completion, when all participants in Part II have completed 12 months of follow-up or have withdrawn from the study.

Definition of analysis population will follow intention-to-treat (ITT) principles including, as much as possible, all enrolled participants evaluated for the outcome(s) being analyzed. An exception will be for safety analyses, wherein participants will be included corresponding to treatment actually received.

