9.3 Major Secondary Analyses

Secondary analyses will be done for two study populations. Participants randomized in Part I or assigned to the abatacept arm in Part II will comprise the enrolled population [N approximately equal to 126 (37 Part I, 89 Part II)]. The overall study population [N approximately equal to 554] will include the enrolled population and 428 patients from the CARRA Registry whose disease extension results provided the control mean in Part II.

Secondary analyses for the enrolled population

Secondary analyses will generally be conducted as planned in Part I, although estimation of treatment effects or treatment by factor differences will be imprecise, since more than 80% of participants in the enrolled population are expected to receive abatacept.

Description of the time to disease extension will include cumulative incidence curves for the composite primary outcome and for the components disease extension, uveitis, and initiation of DMARDs or other biologic medication.

Descriptive analyses will summarize participant and caregiver reported outcomes (continuous outcomes of pain interference, fatigue, upper extremity function, mobility, anxiety, depression and global health PROMIS® modules, medication side effects (JAMAR), and the CHAQ). These outcomes will be measured at baseline and follow-up visits as shown in Table 5, and will be analyzed using a mixed model for repeated measures. Preliminary analyses will be performed to identify a parsimonious covariance structure among the repeated measures. The model will include as fixed effects treatment, time, treatment x time interaction, the baseline value of the outcome and the two stratification variables, the risk categories for polyarthritis and uveitis. Time will be treated as a categorical variable. The restricted maximum likelihood (REML) method of estimation and the Kenward-Roger degrees of freedom correction will be used. Contrasts will be constructed among the model parameters to test specific hypotheses. Overall treatment effect will be assessed by testing the null hypothesis of no treatment difference averaged over time. If the treatment x time interaction is significant at $\alpha=0.10$, additional descriptive tests may be done for treatment differences at specific time-points. Since more than 80% of participants in the enrolled population are expected to receive abatacept, there will be limited statistical power to determine treatment effects on these outcomes.

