9.4 Other Planned Analyses

Other planned analyses for the enrolled population

In addition to assessment of treatment differences in PROs, other secondary outcomes include proportion of children achieving clinically inactive disease and/or remission; number of new joints with arthritis; cumulative number of glucocorticoid joint injections; serious adverse events; juvenile arthritis disease activity (JADAS) scores; elapsed time from enrollment to disease extension, uveitis or initiation of DMARD or other biologic treatment.

Sensitivity analyses will be performed to assess the impact of COVID-19 – including measures taken in response to the pandemic such as telehealth visits, missed visits or oral prednisone use on the primary study endpoint. COVID-19 infections will be included in the safety analyses.

Other planned analyses for the overall population

To be described in a separate SAP.

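### Pooling 18-month Part I with 12-month Part II without a common window gives enrolled usual-care children about 1.38 times the planned observation time on cumulative secondary outcomes

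*Combined protocol and SAP*

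**What the plan says.** Section 9.1 describes two parts with different lengths. For Part I: "Planned duration of the study for each participant was 18 months", made up of 24 weeks of treatment and a further 12 months. Enrollment into Part I has stopped, but "Part I participants will continue follow-up as planned". For Part II: "Planned duration of the study for each participant is 12 months".

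The arms are not spread evenly over the parts. In Part I, "Participants were randomly allocated (1:1) to receive 24 weeks of abatacept plus usual care or usual care alone". In Part II there is no concurrent control: "Part II participants will all be assigned to receive abatacept + usual care".

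Section 9.3 combines about 37 Part I and 89 Part II children into one enrolled population of about 126 and says: "Secondary analyses will generally be conducted as planned in Part I". Section 9.4 lists further outcomes for that population, among them "number of new joints with arthritis; cumulative number of glucocorticoid joint injections; serious adverse events" and the proportion reaching inactive disease or remission. The synopsis and section 8.2.4 add the proportion with polyarthritis or uveitis. None of these places gives a cut-off in time, a person-time rate or an offset. The primary outcome, by contrast, is tied to 12 months in sections 8.1 and 9.2.

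**The concern.** A count of injections or new joints, or a proportion that ever had an event, grows with the time a child is watched. In the enrolled population every usual-care child is planned for 18 months, while about 83% of abatacept children (89 of 107.5 on an even Part I split) are planned for 12. If all available data are counted, part of any arm difference will be a difference in observation time.

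The direction depends on the outcome. Longer observation raises injections, new joints and extension in usual care, which flatters abatacept. It also gives usual care longer to reach inactive disease at least once, which works against abatacept. Section 9.3 warns only of imprecision and limited power. That does not cover this problem, because a wide interval around a shifted estimate still has the wrong centre.

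**Working it through.** **Inputs.** Durations of 18 and 12 months (section 9.1). Part I size: "As of October 29, 2021, 37 participants have been randomized in Part I". Part II: 89 enrolled (sections 9.3 and 9.4.2). The actual Part I split is not given. From 1:1 allocation I assume 18.5 per arm and let usual care range from 17 to 20.

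**The plan's own figures.** 37 + 89 = 126, as in section 9.3. Abatacept share: (18.5 + 89)/126 = 85.3% (86.5% to 84.1% for 17 to 20 usual-care children), consistent with the stated share above 80%.

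**Planned observation time.** Usual care: 18 months. Pooled abatacept: (a × 18 + 89 × 12)/(a + 89), where a is the number of Part I abatacept children.

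| Usual care / abatacept in Part I | Mean months, abatacept | Ratio 18/mean |
|---|---|---|
| 17 / 20 | 1428/109 = 13.10 | 1.374 |
| 18 / 19 | 1410/108 = 13.06 | 1.379 |
| 18.5 / 18.5 | 1401/107.5 = 13.03 | 1.381 |
| 20 / 17 | 1374/106 = 12.96 | 1.389 |

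Using the 80 evaluable Part II children instead of 89 gives 1.36 to 1.38.

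**Counts per child with no drug effect.** With a constant rate and full retention, counts are proportional to time. With 18 usual-care children, 1 − 13.06/18 = 0.27, so abatacept shows about 27% fewer injections or new joints. Seen from the other side, usual care shows about 38% more.

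**If rates fall over time (assumed).** Let the rate halve every h months, so the expected count by month t is proportional to 1 − 2^(−t/h). Use the even split.
- h = 12: usual care 0.646; abatacept (18.5 × 0.646 + 89 × 0.500)/107.5 = 0.525; usual-care excess 23%.
- h = 6: usual care 0.875; abatacept (18.5 × 0.875 + 89 × 0.750)/107.5 = 0.772; usual-care excess 13%.

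**If half of Part I leaves after month 12 (assumed).** Mean time in Part I is 15 months. Abatacept: (18.5 × 15 + 89 × 12)/107.5 = 12.52. Ratio 15/12.52 = 1.20.

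**An ever/never proportion (illustration).** Take 34.3% by 12 months in both arms and a constant hazard. By 18 months the proportion is 1 − 0.657^1.5 = 46.7%. Pooled abatacept would show (18.5 × 46.7% + 89 × 34.3%)/107.5 = 36.4%, a gap of 10.3 points with no drug effect. The 34.3% in section 9.4.2 is for the full composite including systemic medication. For polyarthritis or uveitis alone the rate, and so the gap, would be no larger.

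**With a common 12-month cut-off.** 12/12 = 1.00.

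**The case against.** The strongest reply is that most of the current text points to month 12. Section 8.1 describes joint counts from baseline through month 12, Table 2 ends at the M12 visit, and section 9.2 speaks of a 12-month study. This has some force for new joints and for the extension proportion. But the joint-count sentence sits under the primary outcome, the schedule is that of the current version, and section 9.1 expressly keeps Part I on its longer follow-up. For injections and ever-inactive disease no time limit is stated.

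The reply succeeds for several other outcomes. A reader might infer that serious adverse events are biased too, since section 9.4 lists them without a window. Section 7.6, however, ends their reporting at the Month 12 visit, or 30 days after the last dose on early termination. A reader might also extend the point to patient-reported outcomes and JADAS, but section 9.3 ties the former to Table 5, visits are defined only through M12 (sections 4.1 and 4.3.1), and JADAS can be compared at shared visits. Cumulative incidence curves can handle unequal follow-up by censoring.

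It is also fair to say that the Part I analysis plan is not among the documents. The reference in section 9.3 to doing things as planned in Part I does not show that an 18-month analysis is intended, only that the window is not stated.

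Finally, these contrasts rest on roughly 18 usual-care children, and the plan already calls them imprecise. That limits how much weight they will carry, but it does not remove the bias.

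**Conclusion.** The point holds for four outcomes in the enrolled population: cumulative glucocorticoid joint injections, number of new joints, ever achieving inactive disease or remission, and the proportion with polyarthritis or uveitis. Without a common window, usual care has about 1.38 times the planned observation time of pooled abatacept (1.37 to 1.39). That ratio concerns planned time, not events. The 27% shortfall in counts on abatacept needs a constant rate and complete retention to month 18; under the declining rates assumed above, usual care's excess drops from about 38% to 23% or 13%, and with half of Part I leaving after month 12 the time ratio is about 1.20.

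Three stronger readings are not supported. The primary endpoint is not affected, because its window is 12 months in both parts. The bias does not uniformly favour abatacept, because it reverses for ever-inactive disease. Nor is treatment nearly interchangeable with follow-up length, since about half of Part I received abatacept with the same 18 months planned.

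**What to change.** In sections 9.3 and 9.4, state that these four outcomes are counted only through the 12-month (48-week) point from enrollment for both parts. Report Part I data after month 12 separately, as a description of the randomised cohort. Confirm in the same place that the Month 12 limit for serious adverse events, patient-reported outcomes and JADAS also applies to Part I children.

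A person-time rate would be an alternative for the counts, but it removes the imbalance only if the rate is constant, so the common cut-off is simpler and safer.

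The cost is a change of wording. The one loss is that Part I data after month 12 leave the pooled comparison, though they are still reported.

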9.2 Primary Analysis

The primary outcome is the proportion of participants experiencing disease extension, (development of polyarthritis or uveitis, or initiation of systemic medications during the 12-month period following enrollment). Participants will undergo evaluations for polyarthritis every 3 months during the 12-month duration of the study. Ophthalmological examinations for uveitis will be performed for enrolled participants according to the schedule in Table 3.

The primary analysis will compare the disease extension rate in the group of patients assigned to receive abatacept in Part II to a weighted average of disease extension rates observed in 6 cohorts (total of 428 patients) from the CARRA Registry who would have met the entry criteria for LIMIT-JIA. [See Appendix: Modification of Study Design and Rationale for Discontinuing Randomization to Control Arm]

The primary analysis will use the logistic regression model, $\log(\pi / (1 - \pi)) = \text{TRT}$, where TRT is the assigned treatment arm (abatacept or control). This analysis will test the null hypothesis that the disease extension rates in the abatacept and control arms are equal. The odds ratio with 95% confidence limits will describe the estimated treatment effect.

A secondary analysis of the disease extension rate will include a stratification factor for Part (I or II) and an interaction term (TRT x PART). This analysis will assess the homogeneity of treatment effect between Part I and Part II. Due to the small number of participants randomized to the control arm, statistical power to detect a TRT x PART interaction is limited.

For Parts I and II, the analysis population for the primary endpoint will consist of participants whose disease status is determined at 12 months. In case some participants are not evaluated at 12 months, sensitivity analyses may be performed including simulated data for the participants with unobserved primary outcome. Simulations will be conducted under a variety of assumptions about the distribution of the unobserved outcomes including 1) under the null hypothesis, 2) under alternative hypotheses unfavorable to the abatacept plus usual care treatment arm and, if appropriate, 3) according to plausible patterns determined by taking into account factors such as baseline disease status, length of follow-up, and magnitude and variance of estimated treatment effect from observed data. Non-random patterns of missing data may be considered. If the estimated treatment effects and conclusions from hypothesis testing are generally consistent between the primary and sensitivity analyses, the primary analysis will be considered accurate.

Methods used to account for missing data will be described in more detail in the Statistical Analysis Plan.

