4 STUDY DESIGN

4.1 Overview of Study

The study treatment consists of an open label 24-dose course of weekly subcutaneous (SQ) abatacept (Orencia) plus usual care, versus usual care subject comparators from the CARRA Registry to prevent the development of polyarthritis or uveitis, or initiation of systemic glucocorticoid, DMARD, and/or biologic medication within 12 months of enrollment in children with recent-onset limited JIA. Patients enrolled in the CARRA Registry receiving usual care who meet Limit-JIA inclusion/exclusion criteria will constitute the comparator arm, providing the proportion of children that develop disease extension on usual care alone.

There are 6 study visits: screening, enrollment, approximately month 3 (M3 visit), month 6 (M6 visit), month 9 (M9 visit), and month 12 (M12 visit [end of study]). The screening visit may be combined with the enrollment visit if all procedures can be completed and participant qualifies for the study. Clinical trial visits may occur either in person or via telehealth except for the screening or enrollment visits. One of these visits must be conducted in the clinic. The month 12 end of study visit must also be conducted in the clinic.

In order to enhance study recruitment and timely enrollment, a subset of Limit-JIA US based clinical trial sites will incorporate enhanced cohort identification of potential study participants that incorporates EHR-based algorithms to predict the presence of limited JIA. Specifically, a ‘computable phenotype’ will be utilized to generate screening lists of potentially eligible, recently diagnosed limited JIA patients who may be considered for enrollment. These EHR-based screening lists will then be further reviewed by site staff for study eligibility.

Study participant identification and enrollment using enhanced screening will be compared to use of traditional screening methods alone at this subset of sites. In addition, at a subset of US based sites, all enrolled CARRA Registry participants with JIA will have registry data supplemented by selected EHR data elements, which will be linked by the site and made available in the CARRA Data Warehouse, enabling analyses of registry data completeness.

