4.3 Study Assessment

4.3.1 Schedule of Assessment

Table 2: Schedule of Assessments (All assessments except the ophthalmology exams and screening and enrollment visits may occur in person or via telehealth.)

	Screen Visit	Enrollment Visit (Baseline) (≤45 days)	M3 (+/-2 weeks)	M6 (+/-2 weeks)	M9 (+/-2 weeks)	M12 End of Study ¹ (+/-2 weeks)	Interim Visits ²
Inclusion/Exclusion Criteria	X	X					
Consent/Accent	X						
Demographic Information	X	X					
Enrollment	X ¹⁰	X					
Past Medical Hx (per CARRA registry)	X						
Physical Exam	X	X	X	X	X	X	X
Active Joint Count	X	X	X	X	X	X	X
Concomitant Meds (per CARRA registry)	X	X	X	X	X	X	X
Study Drug Adherence			X	X			
Dose/Instructions		X					
Drug Dispensation		X ¹²	X ¹²				
Ophthalmology Exam ³	X	See Ophthalmology Assessment Table 3 below The 1 st Dose of study drug cannot be administered until after the screening eye exam has confirmed no disease. The M12 End of Study eye exam can be done up to 4 weeks after the end of study visit.					
MyStudies App enrollment		X					
Physician Global		X	X	X	X	X	X
Parent Global		X	X	X	X	X	X
PROMIS® Measures ⁷	X	X	X	X	X	X	X
CHAQ		X		X		X	X
JAMAR		X	X	X			X
Duration of Morning Stiffness (Patient Reported)	X	X	X	X	X	X	X
JADAS		X	X	X	X	X	X
SAEs & ESIs (Per CARRA registry)	X	X	X	X	X	X	X
Quantiferon Gold/TB screen (drug can be administered in the absence of test results. Patient families will be instructed to not administer drug until a	X	X ¹¹					

	Screen Visit	Enrollment Visit (Baseline) (≤ 45 days)	M3 (+/-2 weeks)	M6 (+/-2 weeks)	M9 (+/-2 weeks)	M12 End of Study ¹ (+/-2 weeks)	Interim Visits ²
negative result is confirmed)							
Urine pregnancy screen ⁸		X ⁸	X ⁸	X ⁸	X ⁸	X ⁸	X ⁸
CBC	X ⁵		X ⁴	X ⁴			
HBsAg ⁹	X						
CMP	X ⁵		X ⁴	X ⁴			
ESR/CRP ⁴	X ⁴		X ⁴	X ⁴	X ⁴	X ⁴	
ANA	X ⁶						
HLA-B27, RF, anti-CCP (Per CARRA Registry)	X						
Covid-19 Survey ¹³	The patient/guardian will complete the Covid 19 Survey using the MyStudies App every week before study drug administration.						

¹ End of study visit should be conducted at the end of the follow up period or if the participant discontinues the study for any reason, including development of polyarticular JIA or anterior uveitis, escape from treatment arm, safety concern, or withdrawal of consent.

² Interim visits occur whenever a study participant is evaluated clinically outside of the regularly scheduled study visit schedule for symptoms concerning for active arthritis, new anterior uveitis, or SAEs.

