4.3.3 Recommended Ophthalmology Assessments

The frequency of ophthalmology assessment for each participant depends on the presence or absence of known risk factors for JIA associated uveitis including ANA status and age at onset of JIA as per Table 3 below. Per protocol, a screening ophthalmology exam is *required within 45 days prior to enrollment*. A subject may complete the rheumatology screening visit and then have the screening ophthalmology exam performed after enrollment. In this case, **the 1st Dose of study drug cannot be administered until after the screening eye exam has confirmed no uveitis.**

The Month 12 (end of study) eye exam is also *required; however, it can be obtained up to 4 weeks after the end of study visit.*

The presence of active anterior uveitis will be defined according to the Standardization of Uveitis Nomenclature for Reporting Clinical Data (SUN criteria)⁶²: the presence of 1 or more cells in each 1mm x 1mm slit beam field (Grade 0.5+ or trace cells). During the study, evaluation for anterior uveitis follow SOC intervals described by the Heiligenhaus modification of the American Academy of Pediatrics recommendations⁶³.

Table 3: Recommended Schedule of Ophthalmology Exam

	ANA	Age at JIA Onset	Screen Visit**	M 3	M 6	M 9	M 12***
Oligoarthritis* (Q3 months)	+	≤ 6	X	X	X	X	X
Oligoarthritis* (Q6 months)	+	> 6	X		X		X
Oligoarthritis* (Q6 months)	-	≤ 6	X		X		X
Oligoarthritis* (Q12 months)	-	> 6	X				X
Enthesitis-related arthritis	+ or -	Any	X				X

*Includes ILAR categories of oligoarthritis, psoriatic arthritis (if no current active psoriasis or history of psoriasis), and undifferentiated arthritis.

** Screening ophthalmology exam required within 45 days of enrollment.

*** Month 12 screening required within 4 weeks of End of Study visit.

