4.4 Screening and Pre-Enrollment Procedures

All eligible study participants will be recruited from CARRA Registry sites.

All participants are also consented and enrolled in the CARRA Registry and will have a CARRA Global ID number. Additionally, study participants will be assigned a Limit-JIA study participant number at the time the consent is signed.

For the purpose of this study the term enrolled will be defined as having signed consent. Children with limited JIA who have provided assent if required and whose parent/legal guardians have given written permission will be screened for Limit-JIA. If they meet all inclusion and no exclusion criteria, they will be enrolled into the study. They will concurrently consent and enroll into the CARRA Registry protocol (if not already enrolled in the CARRA Registry). Written or electronic informed consent will be obtained per each enrolling site's or the central IRB's requirements.

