Secondary analyses for the overall study population

Inclusion of data from 428 CARRA Registry patients may provide important information on the impact of treatment on time to disease extension and PROs. Since treatment assignment for the overall study population is not random, it is anticipated that causal inference techniques such as inverse probability or overlap weighting will be useful in determining the comparability of the Registry patients and participants enrolled in LIMIT-JIA.

The timing of evaluations for disease extension and PROs and missing data patterns are expected to differ between participants enrolled in LIMIT-JIA and CARRA Registry patients. Techniques such as multiple imputation may be used to enable modeling of the overall study population.

Details of the analysis of treatment effect for the overall study population will be provided in a separate SAP.

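### The primary comparison sets trial events against Registry events found on a different evaluation timetable, and neither the primary model nor its sensitivity analyses allow for this

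*Combined protocol and SAP*

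**What the plan says.** **How events are found in the trial.** Section 4.1 sets the visits: "There are 6 study visits: screening, enrollment, approximately month 3 (M3 visit), month 6 (M6 visit), month 9 (M9 visit), and month 12". Section 9.2 confirms the joint timetable: "Participants will undergo evaluations for polyarthritis every 3 months during the 12-month duration of the study". Symptom-driven contacts add to this (section 4.3.1, footnote 2 to Table 2): "Interim visits occur whenever a study participant is evaluated clinically outside of the regularly scheduled study visit schedule for symptoms concerning for active arthritis". Eye examinations are not uniformly 3-monthly. Section 9.2 says "Ophthalmological examinations for uveitis will be performed for enrolled participants according to the schedule in Table 3", and Table 3 sets intervals of 3, 6 or 12 months by risk. Section 4.3.3 adds a closing examination, timed from the final visit: "The Month 12 (end of study) eye exam is also *required; however, it can be obtained up to 4 weeks after the end of study". On the mode of visit, section 4.1 says "Clinical trial visits may occur either in person or via telehealth except for the screening or enrollment visits", and it requires the month 12 visit to be in clinic.

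**What the trial is compared with.** Section 9.2 compares Part II with a weighted average of the rates in six Registry cohorts, 428 patients in all. Section 9.4.2 confirms a Wald test in a logistic model with intercept and treatment only.

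**What the plan says about timing.** Section 9.3, under the secondary analyses for the overall population, states of the contrast with Registry patients: "The timing of evaluations for disease extension and PROs and missing data patterns are expected to differ between participants enrolled in LIMIT-JIA". Its response is optional multiple imputation, plus weighting to judge comparability, with details left to a separate SAP.

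**Overlap of the two sources.** Section 4.4 states: "All participants are also consented and enrolled in the CARRA Registry".

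**The concern.** Two of the three components in section 8.1 depend on someone looking. Polyarthritis is a cumulative count of active joints since onset, so a joint that flares and settles between visits counts only if it is examined in time. Uveitis is defined by cells in a slit-lamp beam and cannot be recorded without an eye examination. A 12-month proportion built on these depends on how often, and how, children are examined.

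In a concurrent randomized comparison both arms share a schedule and the problem largely cancels. Part II has no such arm. If trial visits find more events than Registry follow-up would, a real benefit is partly hidden. If they find fewer, for example because joint counts at months 3 to 9 may be done by telehealth, an apparent benefit can arise with no drug effect. The plan recognizes the difference in timing but attaches it only to secondary analyses.

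**Working it through.** **Inputs (section 9.4.2).** Control rate 0.343, n = 428; abatacept rate 0.15, n = 80 evaluable; one-sided alpha 0.025; Wald test of treatment in logistic regression.

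**Method.** For x₁ events of 80 and x₀ of 428:

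z = [ln(x₁/(80−x₁)) − ln(x₀/(428−x₀))] / √(1/x₁ + 1/(80−x₁) + 1/x₀ + 1/(428−x₀))

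Reject for abatacept if z < −1.96. Power is the sum of the two binomial probabilities over the rejection region, so sampling error in the control rate is included.

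**Step 1. Reproduce the plan.** Power at n = 80 is 0.958, against 0.956 in Table 7. The other rows (n = 20 to 70) give 0.327, 0.587, 0.738, 0.835, 0.898 and 0.935, against 0.332, 0.591, 0.742, 0.824, 0.900 and 0.934. Enrollment is 80/0.90 = 88.9, so 89, as stated. Type I error with equal detection is 0.022. The design arithmetic is sound when both sources detect events equally.

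**Step 2. Registry finds fewer events than trial visits would.** Assumption: Registry-type follow-up finds a fraction s of the events that trial visits find, and the abatacept rate under Registry-type follow-up is 15%. The trial then shows 0.15/s if all events depend on examination, or 0.15 × (0.5 + 0.5/s) if only half do (also an assumption).

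| s | Rate, all events affected | Power | Rate, half affected | Power |
|---|---|---|---|---|
| 1.00 | 15.0% | 0.958 | 15.0% | 0.958 |
| 0.90 | 16.7% | 0.910 | 15.8% | 0.937 |
| 0.80 | 18.8% | 0.811 | 16.9% | 0.902 |
| 0.75 | 20.0% | 0.732 | 17.5% | 0.876 |

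**Step 3. Trial finds fewer events than the Registry.** Assumption: no drug effect, and the trial finds a fraction k of what the Registry finds, so it shows 0.343 × k.

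| k | Trial rate | Apparent odds ratio | False-win rate |
|---|---|---|---|
| 1.0 | 34.3% | 1.00 | 2.2% |
| 0.9 | 30.9% | 0.86 | 7.7% |
| 0.8 | 27.4% | 0.72 | 20.8% |

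If only half of events were affected, k = 0.9 and 0.8 would act as 0.95 and 0.90 overall, giving 4.3% and 7.7%.

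**Step 4. Look for an allowance elsewhere.** The sensitivity analyses in section 9.2 simulate outcomes for participants not evaluated at 12 months; they do not address outcomes observed with different intensity. Section 9.4 plans sensitivity analyses of COVID-19 measures, telehealth visits included, on the primary endpoint, but within the enrolled population, which does not align trial with Registry. The treatment-by-part interaction in section 9.2 is acknowledged there to have limited power.

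**The case against.** The strongest counter-case has five parts.

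- **Not every component depends on examination.** Starting systemic medication comes from the medication record, which Table 2 marks as collected per the Registry. This stands. The whole-composite figures are therefore upper bounds for each assumed ratio, which is why the half-affected figures are shown. Study visits can still prompt a medication start.
- **Telehealth is not ignored.** Section 9.4 covers it as a COVID-19 sensitivity analysis, and the month 12 visit is in clinic, so a joint still active then would be found in person. This stands too; mainly transient joints are exposed.
- **The eye schedule may match ordinary care.** Every row of Table 3 has a month 12 examination, and the intervals follow standard-of-care recommendations. Whether the 428 Registry children had those examinations is not stated.
- **The Registry schedule may be documented elsewhere.** Section 9.2 cites an appendix on the design change that is not in the text available, and it may describe how events in the 428 were ascertained. That could narrow the concern, but section 9.3 still expects timing to differ.
- **An alignment analysis can itself bias the result.** Removing trial-only findings or required eye examinations from the abatacept arm alone would delete real events on one side and could favor abatacept. This stands, and it rules out a one-sided remedy.

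A reader might infer that more frequent trial visits must bias the result against abatacept, or that telehealth must bias it in favor. The documents support neither, because they do not give the Registry interval. Nor do they support reading the sample size as wrong: the stated power and enrollment reproduce.

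**Conclusion.** The concern holds as a gap in comparability, not in arithmetic. The plan expects evaluation timing to differ between its two sources, yet the primary comparison has no term, alignment rule or sensitivity analysis for it. The primary odds ratio can therefore be biased, in a direction that cannot be signed from the text available.

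Modest differences in detection would matter: a 20% shortfall in the Registry takes power from 0.958 to 0.81 (0.90 if half of events depend on examination), and a 20% shortfall in the trial takes the false-win rate from 2.2% to 20.8% (7.7% if half). The detection ratios are illustrative assumptions, not estimates. How large the real difference is remains unknown until the Registry visit dates of the 428 are examined.

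**What to change.** In section 9.2, before the first interim look (planned in section 9.5.4 at about n = 32), pre-specify a common-ascertainment sensitivity analysis to be reported beside the primary result.

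1. State the actual visit and eye-examination timing of the 428 Registry patients.
2. Define 12-month event status in both groups by one symmetric rule: the same event definitions, the same sources where both groups have them (Registry uveitis form, medication record, joint counts), and the same assessment windows, set from those Registry visit dates.
3. Apply any thinning of visits or examinations to both groups by the same rule. Do not drop eye-examination findings from the abatacept arm only.
4. Report results by component, and flag each joint count as in person or telehealth.
5. Add a tipping-point analysis giving the detection ratio, in either direction, at which the primary conclusion changes. This avoids an undefined requirement that the two analyses agree.

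**Cost.** Some programming and one flag per joint count, with no new patients or procedures. Section 8.1 puts trial joint counts on a dedicated form, so it must first be checked that matching Registry joint data exist. Somewhat fewer events will be counted. The bias will be reduced, not removed, because trial visits can prompt medication starts and, under section 6.4, discontinuation of study drug once a primary event is found.
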